4 STUDY DESIGN

4.1 OVERALL DESIGN

This is a Phase 3, multicenter, 52-week treatment, parallel-group, double-blind, randomized, placebo-controlled study to investigate the efficacy of dupilumab 300 mg q2w for adults and adolescents/children (≥ 6 to < 12 years) ≥ 60 kg, or dupilumab 200 mg q2w for adolescents/children ≥ 30 kg and < 60 kg, dupilumab 300 mg q4w for adolescents/children ≥ 15 kg and < 30 kg with signs and symptoms of AFRS. The study will primarily investigate the efficacy of dupilumab to reduce disease burden in the sinuses (sinus opacification) by radiographic imaging. In addition, the study will also evaluate efficacy of dupilumab to reduce the need for repeated SCS and/or surgery, nasal polyps burden, clinical symptoms, and explore other measures of disease activity.

Approximately 62 participants (31 per arm) with AFRS who satisfy the inclusion and exclusion criteria will be randomized in a 1:1 ratio to receive either dupilumab or matching placebo:

- Dupilumab 300 mg q2w for all adults, 300 mg q2w for adolescents/children ≥ 60 kg at screening, or 200 mg q2w for adolescents/children ≥ 30 kg and < 60 kg at screening, or 300 mg q4w for adolescents/children ≥ 15 kg and < 30 kg at screening.
- Matched placebo.

Randomization will be stratified first by age (adults versus adolescents/children [≥ 6 years old]). In adults, randomization will be stratified further by time from last surgery (≤ 2 years [including surgery naive participants], > 2 years), disease pattern (unilateral/bilateral in the endoscopy at screening), and country. In adolescents/children, randomization will not be stratified further.

Duration of study period (per participant):

- Screening period (2 to 4 weeks): to determine a participant's eligibility and continue with his/her own background intranasal corticosteroids (INCS) prior to randomization.
- Randomized IMP intervention period (52 weeks ± 3 days): to randomize the participants into a treatment arm and treat with dupilumab or placebo dose regimen.
- Follow-up period (12 weeks ± 5 days): to continue to collect data for PK, immunogenicity, safety, and efficacy after the participant has completed the randomized IMP intervention period.

The total duration of study participation for participants that complete the randomized treatment period and posttreatment follow-up is approximately 68 weeks. The schedule of the visits is described in the specific flow-chart in [Section 1.3](#).

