6.1 STUDY INTERVENTION(S) ADMINISTERED

Table 2 - Overview of study interventions administered

ARM name	Dupilumab	Placebo
Intervention name	Dupilumab 200 mg or Dupilumab 300 mg	Placebo
Type	Biological	Other
Dose formulation	Dupilumab 200 mg: A 175 mg/mL dupilumab solution in a pre-filled syringe to deliver 200 mg in 1.14 mL. or Dupilumab 300 mg: A 150 mg/mL dupilumab solution in a pre-filled syringe to deliver 300 mg in 2 mL.	Placebo matching dupilumab 200 mg will be supplied as an identical formulation to the active 200 mg formulation without dupilumab, in a pre-filled syringe to deliver placebo in 1.14 mL. or Placebo matching dupilumab 300 mg will be supplied as an identical formulation to the active 300 mg formulation without dupilumab, in a pre-filled syringe to deliver placebo in 2 mL.
Unit dose strength(s)	200 mg or 300 mg	0 mg
Dosage level(s)	One injection of 200 mg q2w for adolescents/children \geq 30 kg and <60 kg at screening or One injection of 300 mg q2w for all adults and for adolescents/children weighing \geq 60 kg at screening or One injection of 300 mg q4w for adolescents/children \geq 15 kg and <30 kg at screening	One injection of placebo matching 200 mg q2w for adolescents/children \geq 30 kg and <60 kg at screening or One injection of placebo matching 300 mg q2w for all adult participants and for adolescents/children weighing \geq 60 kg at screening or One injection of placebo matching 300 mg q4w for adolescents/children \geq 15 kg and <30 kg at screening
Route of administration	Subcutaneous injection	Subcutaneous injection
Use	Experimental	Experimental
IMP	IMP	IMP
Packaging and labeling	Each dose of dupilumab will be supplied as 1 glass pre-filled syringe packed in a participant kit box. Both glass pre-filled syringe and box will be labeled as required per country requirement	Each dose of placebo will be supplied as 1 glass pre-filled syringe packed in a participant kit box. Both glass pre-filled syringe and box will be labeled as required per country requirement

The IMP will be administered every 14 ± 3 days (q2w) or 28 ± 3 days (q4w) during the 52-week treatment period (with the last IMP administration at Week 50 for q2w administrations and at Week 48 for q4w administrations).

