8.3.1 Time period and frequency for collecting AE and SAE information

All SAEs will be collected from the signing of the ICF/assent form until the EOS visit at the time points specified in the SoA ([Section 1.3](#)).

All SAEs and adverse events of special interest (AESI) will be recorded and reported to the Sponsor or designee immediately and under no circumstance should this exceed 24 hours, as indicated in Appendix 3 ([Section 10.3](#)). The Investigator will submit any updated SAE data to the Sponsor within 24 hours of it being available.

Investigators are not obligated to actively seek AE or SAE after conclusion of the study participation. However, if the Investigator learns of any SAE, including a death, at any time after a participant has been discharged from the study, and he/she considers the event to be reasonably related to the study intervention or study participation, the Investigator must promptly notify the Sponsor.

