- The **treatment-emergent (TE) period** is defined as the period from the first IMP administration to the last IMP administration +98 days. The treatment-emergent period includes the following 2 periods:

- The **on-treatment period** is defined as the period from the first IMP administration to the last administration of the IMP +14 days for adults and adolescents/children ≥ 30 kg at screening or 28 days for adolescents/children ≥ 15 kg and < 30 kg at screening.
- The **residual treatment period** is defined as the period from the end of the on-treatment period to the end of the treatment-emergent period.
- The **post-treatment period** is defined as the period from the end of the treatment-emergent period.

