- Number (%) of participants with any AE leading to death
- Number (%) of participants with any TEAE leading to permanent study intervention discontinuation
- Number (%) of participants with any TEAE related to IMP reported by investigator
- Number (%) of participants with any TEAE by maximum intensity, corrective treatment, and final outcome
- Number (%) of participants with any TEAE adjusted by the exposure duration
- Number (%) of participants with injection site reactions by the related injection.
- Number (%) of participants with different number of injection site reactions.

In addition, AESIs reported by the investigator in eCRF will be summarized separately.

Analysis of exposure-adjusted incidence rate

If the cumulative duration of treatment exposure is imbalanced between dupilumab and placebo, then the number of participants with at least one TEAE per 100 participant-years will be provided for the below summaries:

- Overview of adverse events profile
- TEAE by primary SOC and PT
- Common TEAE ($\geq 5\%$ in any group) by primary SOC and PT
- Treatment-emergent SAE by primary SOC and PT
- TEAE leading to permanent intervention discontinuation by primary SOC and PT
- Treatment-emergent AESI and other selected AE grouping events by category and PT

For participants with an event, the number of participant-years will be censored at time of the first event; for participants without an event, the number of participant-years corresponds to the length of the treatment-emergent period.

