3.8 INTERIM ANALYSES

There is no interim analysis planned as part of this study.

A primary database lock will be performed when all randomized participants have completed or discontinued their treatment phase. Final analyses in the CSR will be based on all data collected up to this database lock.

[figure not shown]
The database will be updated at the end of the study for all participants to include the posttreatment follow-up information and updates for the events previously ongoing at the time of the primary lock. Additional data between this database lock and last participant completing last visit will be summarized in a CSR addendum.

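### Exposure-adjusted AE rates count event-free time to last dose +98 days with no cap at study exit, death or primary lock, so they are modestly understated

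*SAP*

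**What the plan says.** SAP 3.6.2 plans rates per 100 participant-years for several AE summaries, including SAEs, TEAEs leading to discontinuation, and AESIs. They are produced only on a condition: "If the cumulative duration of treatment exposure is imbalanced between dupilumab and placebo". No threshold for imbalance is given.

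The denominator has two parts:
- With an event: "For participants with an event, the number of participant-years will be censored at time of the first event".
- Without an event: "for participants without an event, the number of participant-years corresponds to the length of the treatment-emergent period".

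SAP 3.1 says that the treatment-emergent period "is defined as the period from the first IMP administration to the last IMP administration +98 days". Neither section bounds it by the end of a participant's observation.

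Observation can end sooner under three provisions:
- Protocol 7.2 takes a withdrawing participant out of the study at that time, with an early end-of-study visit if possible.
- Protocol 8.3.1: "All SAEs will be collected from the signing of the ICF/assent form until the EOS visit".
- SAP 3.8: "A primary database lock will be performed when all randomized participants have completed or discontinued their treatment phase". The CSR uses data up to that lock, and later follow-up goes to a CSR addendum.

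SAP 3.6.2 also lists, for each AESI and other AE grouping, a TEAE count adjusted by exposure duration. That line is not tied to the imbalance condition and states no denominator rule.

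**The concern.** Person-time in an incidence rate should be time during which an event would have been recorded. Days after a participant has left the study, has died, or has passed the data cut can enlarge the denominator but cannot add to the numerator. The direction of the error is therefore known: rates are too low.

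What is at stake is the accuracy of a safety table whose purpose is to correct for unequal exposure. If study exits are unequal between arms, the correction brings in an error of its own that differs by arm. No efficacy result is involved, and the plain number and percentage tables are not affected.

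**Working it through.** The documents state no AE rate, total person-time or dropout rate, so there is no planned figure to reproduce. The check is direct person-time arithmetic.

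**Inputs from the documents.** The tail is 98 days (SAP 3.1). Protocol 6.1 sets the dosing end, "with the last IMP administration at Week 50 for q2w administrations and at Week 48 for q4w administrations". The end-of-study visit is at Week 64, 12 weeks after Week 52 (Protocol 1.3 and 4.1). Allocation is 1:1 with 31 per arm.

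**Completers.** For q2w, Week 50 + 98 days (14 weeks) = Week 64, which is the end-of-study visit. For q4w, Week 48 + 14 weeks = Week 62. A completer followed to Week 64 adds no unobserved time, apart from the 5-day visit window. The full q2w length is 50 × 7 + 98 = 448 days.

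**Study exits.** Assumptions, not in the documents: a share w of the arm leaves the study, the last dose is at day t (84, 182 or 266), and exit follows g days later (0 or 14).
- Counted = (1 − w) × 448 + w × (t + 98)
- Observed = (1 − w) × 448 + w × (t + g)
- Understatement = 1 − observed/counted = w × (98 − g)/counted

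Example with w = 0.30, t = 182, g = 0: counted = 313.6 + 84.0 = 397.6; understatement = 29.4/397.6 = 7.4%.

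| Share leaving | t = 182 (g = 14 to 0) | t = 84 to 266 (g = 14 to 0) |
|---|---|---|
| 5% | 1.0–1.1% | 1.0–1.1% |
| 10% | 1.9–2.3% | 1.9–2.3% |
| 20% | 4.1–4.7% | 3.9–5.0% |
| 30% | 6.3–7.4% | 6.0–8.0% |

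These figures treat every participant as event-free. Allowing for censoring at the first event changes little. With w = 0.30, t = 182 and g = 14, the understatement is about 6.3% at true rates of 2 to 50 per 100 participant-years and 5.3% at 200.

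**Primary lock.** A q2w participant who reaches Week 52 on the lock date is counted for 448 days against 364 observed. That is 84 days too many, and 1 − 364/448 = 18.75% for that participant. Only completers randomized within about 12 weeks of the last one are truncated, by 42 days on average if entry is even. With 5 to 20% of an arm in that position (assumed), the arm-level understatement is 0.05 × 42/448 = 0.5% to 0.20 × 42/448 = 1.9%.

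As a rough anchor, the first randomization was on 21 May 2021 (SAP version history), and entry criteria were still being changed on 1 March 2023, 649 days or about 93 weeks later. If enrolment was uniform over at least that span (assumed), at most about 62 × 12/93 = 8 of 62 participants (13%) are truncated.

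**Rate ratio.** With equal true rates and 10% versus 30% leaving at t = 182, the ratio of the low-exit arm to the high-exit arm is:
- g = 0: (1 − 0.0227)/(1 − 0.0739) = 1.055
- g = 14: (1 − 0.0195)/(1 − 0.0634) = 1.047

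**Timing matters as well as number.** An arm with 30% leaving 80 days after last dose is understated by 0.3 × 18/397.6 = 1.4%. An arm with 10% leaving at last dose is understated by 0.1 × 98/431.2 = 2.3%.

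**The case against.** The best reply is that stopping treatment is not the same as leaving the study. The condition for these rates is unequal treatment exposure. Protocol 7.1.1 keeps participants who stop IMP in the study and encourages them to attend the remaining visits. Surgery forces permanent discontinuation of IMP, but these participants still have an end-of-treatment assessment and return visits (Protocol 8.1.2). If they are observed for 98 days after last dose, they add no error. Protocol 7.2 expects withdrawal from the study to be uncommon. This stands.

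It rules out two stronger readings that a reader might infer. One is that rates are always understated most in the arm with more withdrawals. That needs exits from the study, not treatment stops, and similar timing, as the last calculation shows. The other is that the exposure trigger guarantees a differential bias. It identifies a setting where study exits may differ, but exposure can be unequal with no difference in exits.

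A reader might also construct a much larger effect. Suppose 2 versus 8 of 31 leave on Day 71 after a last dose on Day 57, and 10 per arm are exactly at Day 364 at the lock. Counted against observed participant-years are then 36.4 versus 33.7 and 31.6 versus 27.5, inflations of 8% and 15%. The arithmetic is right, but nothing in the documents supports those dropout or lock numbers.

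Three further points reduce the weight of the issue:
- An early end-of-study visit is sought at withdrawal, and related SAEs learned of later must still be reported (Protocol 8.3.1), so capture after exit is not always nil.
- SAP 3.6 makes safety analysis descriptive without testing, and no rate ratio is specified.
- With 3 versus 3 events, for example, an approximate 95% interval for a rate ratio is exp(±1.96 × √(1/3 + 1/3)), about 0.2 to 5.0, far wider than the error.

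Programmers may apply a cap by convention, but the SAP does not say so. The CSR addendum will hold later data, but the SAP does not say that these rates are recomputed there.

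**Conclusion.** The point holds as a minor one. Read literally, the SAP puts unobserved days in the denominator for event-free participants who leave the study within 98 days of last dose or are still in follow-up at the primary lock. The effect is always downward.

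Under the assumed inputs (5 to 30% leaving, last dose Day 84 to 266, exit 0 to 14 days later), an arm's rate is understated by about 1 to 8%. The lock adds about 0.5 to 1.9% if 5 to 20% of an arm is truncated by 42 days on average, roughly the same in both arms under 1:1 randomization. A between-arm distortion of about 5 to 6% needs a contrast such as 10% versus 30% leaving the study with similar timing. The documents neither state nor imply such a contrast.

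This does not threaten the trial's safety conclusions. It is an incorrect denominator rule in a conditional, descriptive output, and it is easy to put right.

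**What to change.** In SAP 3.6.2, replace the rule for participants without an event. Their time should run from first dose to the earliest of last dose +98 days, the end-of-study or last-contact date, death, and the primary lock cut-off date. The rule for participants with an event can stay.

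Apply the same person-time rule to the AESI and AE-grouping summaries adjusted by exposure duration, which currently state no denominator.

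The cost is one sentence and one derived end date. No new data, protocol change or additional analysis is needed.

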3.6.3 Additional safety assessments

3.6.3.1 Laboratory variables and vital signs

The following laboratory variables and vital signs will be analyzed. They will be converted into standard international units.

- Hematology:
 - Red blood cells and platelets and coagulation: hemoglobin, hematocrit, red blood cell count, platelet count
 - White blood cells: white blood cell count, neutrophils, lymphocytes, monocytes, basophils, eosinophils

- Clinical chemistry:
 - Metabolism: glucose, total cholesterol, total protein, albumin, creatine phosphokinase
 - Electrolytes: sodium, potassium, chloride, bicarbonate
 - Renal function: creatinine, blood urea nitrogen, uric acid
 - Liver function: alanine aminotransferase, aspartate aminotransferase, alkaline phosphatase, lactate dehydrogenase, total bilirubin
- Urinalysis: specific gravity, pH, glucose, protein, blood, ketones, bilirubin, urobilinogen, nitrite, and leukocyte esterase. If blood or protein is abnormal, microscopic examination will be performed by the central laboratory.
- Vital signs: pulse rate, systolic and diastolic blood pressure measured in a semi-supine or sitting position after 5 minutes rest, weight, respiratory rate, temperature and height (at each visit for pediatric participants, and at screening visit for adult participants)

Data below the lower limit of quantitation/detection limit (LLOQ) will be replaced by half of the LLOQ, data above the upper limit of quantification will be replaced by ULOQ value.

Quantitative analyses

When relevant, for laboratory variables and vital signs above, descriptive statistics for results and changes from baseline will be provided for each analysis window, the last value and the worst value (minimum and/or maximum value depending on the parameter) during the on-treatment period. These analyses will be performed using central measurements only for laboratory variables.

For all parameters, mean changes from baseline with the corresponding standard error will be plotted over time.

Analyses according to PCSA

Potentially clinically significant abnormality (PCSA) analyses will be performed based on the PCSA list currently in effect at Sanofi at the time of the database lock. For parameters for which no PCSA criteria are defined, similar analyses will be done using the normal range, if applicable.

Analyses according to PCSA will be performed based on the worst value during the treatment-emergent period, using all measurements (either local or central, either scheduled, nonscheduled or repeated).

For laboratory variables and vital signs above, the incidence of participants with at least one PCSA during the treatment-emergent period will be summarized regardless of the baseline level and according to the following baseline status categories:

- Normal/missing
- Abnormal according to PCSA criterion or criteria

Additional analyses for drug-induced liver injury

The following additional analyses will be performed for potential drug-induced liver injury:

- Time to onset of the initial alanine aminotransferase (ALT) or aspartate aminotransferase (AST) elevation ($>3 \times \text{ULN}$) and total bilirubin elevation ($>2 \times \text{ULN}$) during the treatment-emergent period will be analyzed using Kaplan-Meier method.
- A graph of the distribution of peak values of ALT versus peak values of total bilirubin during the treatment-emergent period will be provided.
- For each liver function test (eg, ALT), participants having experienced a PCSA (eg, ALT $>5 \text{ ULN}$) will be summarized using the following categories: Returned to baseline PCSA status (or returned to value $\leq \text{ULN}$ in case of missing baseline) before last IMP dose, Returned to baseline PCSA status after last IMP dose, Never returned to baseline PCSA status, No assessment after elevation. This summary will be performed by categories of elevation (ALT $>3, >5, >10, >20 \text{ ULN}$).

3.7 OTHER ANALYSES

3.7.1 Other variables and/or parameters

3.7.1.1 PK analyses

Predose serum dupilumab concentrations at Visit 2 (Day 1), dupilumab trough levels at Week 12, Week 24, Week 52 and posttreatment serum dupilumab at the End of Study (EOS) visit will be provided.

Serum concentrations of dupilumab will be summarized in the PK population by actual intervention group using arithmetic and geometric means, SD, standard error of the mean (SEM), coefficient of variation (CV), minimum, median and maximum per sampling time. If date and/or time of the drug injection and/or sampling is missing, then the concentration will not be taken into account. For drug-treated participants, where concentration values are below the LLOQ, one-half of the LLOQ will be used. Values will be expressed in the tables with no more than three significant figures. For participants in the placebo group, concentration values below the LLOQ will be taken into account with a plasma concentration considered equal to 0.

These analyses will also be performed by age subgroup ($<18, \geq 18$ years) and by dose regimens/age subgroup. Only listing will be provided for participants of <18 years receiving dupilumab, if the number of relevant participants is not sufficient (ie, ≤ 1) for descriptive analyses.

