The 52-week treatment duration is considered sufficient for efficacy evaluation based on the efficacy results from pivotal dupilumab studies in CRSwNP. Dupilumab 300 mg q2w demonstrated statistically significant and clinically meaningful improvement across all primary and multiplicity-adjusted secondary outcome measures at Week 24 and at Week 52. Early beneficial effect was seen from Week 2 to Week 4, followed by a progressive improvement through 52 weeks. The 52-week duration is also appropriate to evaluate safety considering the extensive safety experience with the related condition of CRSwNP. The posttreatment 12-week follow-up period is based on the expected PK of dupilumab after the last dose, ie, the time for systemic concentrations to decline to non-detectable levels in most participants.

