Any abnormal laboratory value will be immediately rechecked for confirmation within a reasonable timeframe as assessed by the Investigator before making a decision of definitive discontinuation of the IMP for the concerned participant.

Handling of participants after definitive intervention discontinuation

If participants no longer wish to take the IMP, they will be encouraged to remain in the study.

The Investigators should discuss with them key visits to attend. The value of all their study data collected during their continued involvement will be emphasized as important to the public health value of the study.

Participants who withdraw from the study intervention should be explicitly asked about the contribution of possible AEs to their decision, and any AE information elicited must be documented.

Participants will be followed-up according to the study procedures specified in this protocol up to the scheduled date of study completion, or up to recovery or stabilization of any AE to be followed-up as specified in this protocol, whichever comes last.

Participants who discontinue the study intervention prematurely (prior to completing the 52-week treatment period) will perform, as soon as possible, the early termination visit with all assessments normally planned for the end of treatment (EOT) Visit (Visit 7) (refer [Section 8.1.1](#)) including a pharmacokinetics sample, if appropriate, to assure a complete clinical assessment in close temporal proximity to the premature termination of study treatment is available.

In addition, and to allow assessment of participant outcomes over the stipulated study period, participants will be asked and encouraged to complete all remaining study treatment visits, and participate in all assessments according to the visit schedule with a ± 3 day window. Under exceptional circumstances when a participant cannot come to the site for a scheduled visit, a phone contact can be made. During the phone contact, at least information about AEs, concomitant medication, and status of AFRS should be collected.

All cases of definitive intervention discontinuation must be recorded by the Investigator in the appropriate pages of the eCRF when considered as confirmed.

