5.4 APPENDIX 4 DATA HANDLING CONVENTIONS

Analysis windows for time points

The following analysis windows will decide how the scheduled and/or unscheduled visits will be used in the by-visit analyses of efficacy, safety, PK and ADA variables.

A measurement (scheduled or unscheduled) will be used if it is available and measurement date is within the analysis window.

After applying these time windows, if multiple assessments are associated to the same time point, the closest from the targeted study day will be used. If the difference is a tie, the value after the targeted study day will be used. If multiple valid values exist within a same day, then the first value of the day will be selected.

If there is no measurement for a given parameter in an analysis window, data will be considered missing for the corresponding visit.

Efficacy assessment

For the efficacy assessment, the reference date for the derivation of relative days of events or findings will be the day of first administration of intervention. If a participant was randomized but not treated, the reference date of efficacy assessment will be the randomization day for that participant.

For efficacy variables other than daily eDiary data (Nasal symptom diary), all available values of scheduled measurements will be assigned to the appropriate visit window according to [Table 7](#).

Table 7 - Analyses window definition for efficacy variables

Scheduled visit post baseline	Targeted study day	Analysis window in study days			
		Nasal Endoscopy, SNOT-22	CT scan	UPSIT	VAS for rhinosinusitis
Week 2 (Visit 3)	15			1+ to 49	1+ to 49
Week 12 (Visit 4)	85	1+ to 126		50 to 126	50 to 126
Week 24 (Visit 5)	169	127 to 210	1+ to 266	127 to 266	127 to 210
Week 36 (Visit 6)	252	211 to 307			211 to 307

Scheduled visit post baseline	Targeted study day	Analysis window in study days				
		Nasal Endoscopy, SNOT-22	CT scan	UPSiT	VAS for rhinosinusitis	
Week 52 (Visit 7)	364	308 to 405	>266	267 to 405	308 to 405	
Week 64 (Visit 8)	448	>405		>405	>405	

Study days are calculated considering Day 1 as the day of first administration of intervention. For participants randomized but not treated, the randomization day is considered as Day 1.

1: up to 1st dose date/time; 1+: after 1st dose date/time;

For daily eDiary data (Nasal symptom diary), the time period used to calculate the monthly average score is summarized in [Table 8](#) below.

Table 8 - Monthly average of daily nasal symptom diary variables

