Analysis visit	Targeted study day	Day range for calculating monthly average score
Week 4	29	2-29
Week 8	57	30-57
Week 12	85	58-85
Week 16	113	86-113
Week 20	141	114-141
Week 24	169	142-169
Week 28	197	170-197
Week 32	225	198-225
Week 36	253	226-253
Week 40	281	254-281
Week 44	309	282-309
Week 48	337	310-337
Week 52	365	338-365
Week 56	393	366-393
Week 60	421	394-421
Week 64	449	422-449

Study days are calculated considering Day 1 as the day of first administration of intervention. For participants randomized but not treated, the randomization day is considered as Day 1.

Safety assessment

For the safety assessment, the reference date for the derivation of relative days of events or findings will be the date of first administration of intervention. Selected safety variables will be summarized by the analysis window defined in [Table 9](#) for the by visit descriptive analysis.

Table 9 - Analyses window definition for safety variables

Scheduled visit post baseline	Targeted study day	Analysis window in study days	
		Vital signs	Laboratory (hematology, biochemistry, urinalysis)
Week 12 (Visit 4)	85	1+ to 126	1+ to 126
Week 24 (Visit 5)	169	127 to 210	127 to 266
Week 36 (Visit 6)	252	211 to 307	
Week 52 (Visit 7)	364	308 to 405	267 to 405
Week 64 (Visit 8)	448	>405	>405

Study days are calculated considering Day 1 as the day of first administration of intervention.

1+: up to 1st dose date/time; 1+: after 1st dose date/time;

Pharmacokinetics/immunogenicity/biomarker assessment

For the pharmacokinetics/immunogenicity/biomarker variables summary, the reference date for the derivation of relative days of measurements will be the date of first administration of intervention. Pharmacokinetics/immunogenicity/biomarker variables will be summarized by the analysis window defined in [Table 10](#) for the by visit descriptive analyses.

Table 10 - Analyses window definition for PK/ADA/biomarker variables

Scheduled visit post baseline	Targeted study day	Analysis window in study days	
		PK, ADA	Serum total IgE and fungal specific IgE,
Week 12 (Visit 4)	85	1+ to 126	1+ to 126
Week 24 (Visit 5)	169	127 to 266	127 to 266
Week 36 (Visit 6)	252		
Week 52 (Visit 7)	364	267 to 405	>266
Week 64 (Visit 8)	448	>405	

Study days are calculated considering Day 1 as the day of first administration of intervention.

1+: up to 1st dose date/time; 1+: after 1st dose date/time;

Unscheduled visits

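### The Week 12, 24 and 52 dupilumab trough summaries carry no on-treatment condition, so washout samples from participants who stopped IMP enter them

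*SAP*

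**What the plan says.** SAP 3.7.1.1 promises "dupilumab trough levels at Week 12, Week 24, Week 52" and, as a separate item, the post-treatment level at the End of Study visit. The plan therefore means to keep troughs and post-treatment levels apart, but it does not define a trough. Its one exclusion is a completeness rule: "If date and/or time of the drug injection and/or sampling is missing, then the concentration will not be taken into account". For dupilumab-treated participants, "where concentration values are below the LLOQ, one-half of the LLOQ will be used", and these values go into the arithmetic and geometric means per sampling time.

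The choice of sample is left to SAP Appendix 4 (5.4): "Pharmacokinetics/immunogenicity/biomarker variables will be summarized by the analysis window defined in" Table 10. The general rule there is "A measurement (scheduled or unscheduled) will be used if it is available and measurement date is within the analysis window". If several samples fall in a window, the one closest to the target day is kept. The PK windows are: after the first dose to Day 126 (Week 12), Days 127 to 266 (Week 24) and Days 267 to 405 (Week 52).

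The PK population (SAP Table 3) asks only for one post-baseline result in a participant who did not receive placebo alone. SAP 3.1 defines an on-treatment period: last dose +14 days for q2w dosing, +28 days for q4w. SAP 3.7.1.2 uses it to classify ADA responses. SAP 3.7.1.1 does not use it.

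Under Protocol 7.1.1, after definitive discontinuation "participants will be asked and encouraged to complete all remaining study treatment visits". The Schedule of Activities (Protocol 1.3) places PK sampling at Weeks 12, 24 and 52. Protocol 4.2 bases the 12-week follow-up on "the time for systemic concentrations to decline to non-detectable levels in most participants".

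**The concern.** A trough is the level just before the next dose is due in someone still being dosed. A sample taken months after the last injection measures washout. The stated rule puts both in the same row under the same label.

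Serum concentration over time is a listed secondary endpoint. Low off-drug values lower the trough means and widen the spread, most of all in the summaries by age and by regimen within age. SAP 3.7.1.1 drops to a listing for participants under 18 only when there is at most one, so a group of two can be summarised.

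SAP 3.7.1.2.1 also plans plots of concentration against visit by ADA variables. There, a low value caused by stopping IMP looks like ADA-related loss of exposure if the participant is ADA positive. If the participant is ADA negative, it can hide such a loss.

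**Working it through.** **1. The plan's own windows.** Table 10 targets are Days 85, 169, 364 and 448. Midpoints: (85+169)/2 = 127; (169+364)/2 = 266.5; (364+448)/2 = 406. These reproduce the cut points 126/127, 266/267 and 405. The windows are simply midpoints between visits and carry no dosing information. Their lengths are about 126, 140 and 139 days, against a 7-day (±3) visit window: 18 to 20 times as long.

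**2. Time since last dose at later visits.** Formula: visit day minus last-dose day, for a q2w participant who stops and keeps attending.

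| Last dose | Week 24 (Day 169) | Week 52 (Day 364) |
|---|---|---|
| Week 12, Day 85 | 84 days | 279 days |
| Week 24, Day 169 | pre-dose sample, a true trough | 195 days |
| Week 38, Day 267 | on treatment | 97 days |
| Week 50, Day 351 (as planned) | on treatment | 13 days |

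The protocol's follow-up visit on Day 448 comes 448 − 351 = 97 days after the planned last q2w dose. A value at 84 days is close to the stated washout time. Values at 97 days or more have reached it, so half the LLOQ is the likely entry.

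**3. Which sample is kept.** For a last dose on Day 267, the early end-of-treatment sample falls at about Day 281, which is 14 days after dosing and still on treatment. Both Day 281 and Day 364 lie in the Week 52 window. Their distances from target are 83 and 0 days, so the rule discards the true trough and keeps the washout value.

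**4. Size.** Assumptions not in the documents: 31 dupilumab participants all contribute; true troughs are R times half the LLOQ, with R from 100 to 2000; k participants are washed out to half the LLOQ.

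- Geometric mean is multiplied by R^(−k/31).
- Arithmetic mean is multiplied by (31−k)/31 + k/(31R).

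| k | Geometric, R = 100 | Geometric, R = 2000 | Arithmetic |
|---|---|---|---|
| 1 | 0.86 | 0.78 | 0.97 |
| 3 | 0.64 | 0.48 | 0.90 |

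In a subgroup of two with one washed-out value, the geometric factor is R^(−1/2), or 0.10 to 0.02. The arithmetic factor is about 0.5. The median of two values is their mean, so it gives no protection there.

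**5. Event-triggered samples.** Protocol 8.5.1.3 allows PK sampling at the onset of certain events. Against the Day 364 target, an event sample on Day 330 loses to a scheduled Day 364 sample. One on Day 363 displaces a scheduled Day 367 sample. One on Day 300 is used if it is alone in the window.

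**The case against.** The strongest reply is that most of the data are sound and the table is only descriptive. Scheduled samples are drawn before IMP (Schedule of Activities, footnote s), so participants dosed on schedule do give true troughs. The protocol expects definitive discontinuation to be rare. SAP 3.7.1.1 also reports the median, which one to three values among 31 barely move, and the minimum, which would expose such values. Individual concentration plots are planned, and population PK may be reported separately. All of this stands, and it limits the harm. It does not make a sample taken 279 days after dosing a trough. Nor is the wide reading needed to serve the concentration-over-time endpoint, because the SAP itself labels these rows trough and has a separate post-treatment summary.

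A reader might infer more than the documents support:

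- *That any sample in the window is used, and event-triggered samples routinely.* One value per window is kept, so event samples enter only occasionally. The route is also not fully clear: the opening of Appendix 4 admits unscheduled measurements, but its paragraph on unscheduled visits names only laboratory data and vital signs.
- *That End of Study samples from people who leave the study fill the trough rows after 12 weeks of washout.* Protocol 7.2 places the early End of Study visit at the time of leaving. Those who stay have a sample at the scheduled visit, nearer the target day.
- *That the dose justification is undermined.* Protocol 4.3 rests on PK already known from other populations, not on this table.

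**Conclusion.** The point holds for washout samples. Applied as written, the SAP puts concentrations taken long after IMP was stopped into rows labelled trough, and in some cases prefers them to an available on-treatment sample. The bias is downward. It falls mainly on the geometric mean and the small age and regimen subgroups, and it mixes stopping IMP with a possible ADA effect in the plots.

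The size cannot be fixed from the documents, which give neither the LLOQ nor the expected trough nor the number who will stop and keep attending. Under the assumptions above, one washed-out value among 31 lowers the geometric mean by about 14-22% and the arithmetic mean by about 3%; three lower them by about 36-52% and 10%. If some off-drug values are still measurable, the effect is smaller. PK concentration is not in the testing hierarchy of SAP 3.5, so the primary analysis, power and type I error are untouched. The change should be made, but it concerns descriptive PK only.

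**What to change.** In SAP 3.7.1.1, limit the Week 12, 24 and 52 trough rows, and in 3.7.1.2.1 the concentration-by-ADA plots, to scheduled-visit samples taken while the participant is still on IMP. Apply this condition before the closest-to-target choice.

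Use the SAP's existing on-treatment period, extended by the protocol's ±3-day dosing and ±3-day visit tolerances: last dose +14+3+3 = 20 days for q2w and +28+3+3 = 34 days for q4w. This keeps compliant Week 52 samples. The planned gaps are 364 − 351 = 13 days (q2w) and 364 − 337 = 27 days (q4w), or at most 19 and 33 days with both tolerances. The period runs to the last administration overall, so a participant who misses one dose and resumes also stays in.

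Do not require that a dose follow the sample: none follows Week 52, and that row would empty.

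Summarise samples after IMP discontinuation separately, by time since last dose, and list event-triggered samples only.

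The cost is SAP wording and one derived variable, days since last injection; SAP 3.7.1.1 already requires the injection and sampling dates. The downside is slightly fewer values in each trough row.
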